Recent advances of glucose sensors have motivated the research towards closed-loop delivery systems to automatically regulate glucose levels. The closed-loop system is composed of three components: a glucose sensor, an infusion pump, and a dosing algorithm to control how much insulin is delivered based on the sensor readings. Although insulin-alone closed-loop systems significantly improve glucose control compared to conventional pump therapy, they still do not normalize postprandial glucose levels. Patients treated with current insulin-only closed-loop systems maintain glucose levels in the target range 70-75% of the time, but spend 20-25% (i.e., 5-6 hours per day) of the time in hyperglycemia, particularly postprandially [5].

A closed-loop system that delivers both insulin and pramlintide, based on glucose sensor readings, has the potential to better normalize glucose levels. Weinzimer et al. [6] studied the acute effect of pramlintide on the performance of closed-loop delivery, and found that adding pramlintide to the closed-loop system improves glucose control, especially postprandially. Sherr et al. [7] analyzed the chronic effect of pramlintide given as a prandial bolus, and observed that adding pramlintide to the closed-loop system had a 39% reduction in peak postprandial plasma glucose levels, a significant delay in the time to peak plasma glucose level as well as overall a significantly greater time in target levels (3.9 - 10 mmol/L) during daytime hours. In both these studies, pramlintide was delivered at meal times only. In this protocol, we aim to assess the efficacy of the simultaneous, closed-loop, basal-bolus

infusion of pramlintide and insulin with a fixed (i.e., mimicking co-formulation) in controlling glucose levels.

Co-administration of pramlintide at mealtimes along with rapid-acting insulin may lead to an immediate post-prandial plasma sugar reduction followed by a delayed hyperglycemia [8]. The decrease in blood sugar levels in the early postprandial period are due to the faster action time of pramlintide combined with the fast action of rapid-acting insulin. Literature data suggests that the pharmacodynamics of regular insulin may better match the effect of pramlintide compared to the pharmacodynamics of fast-acting insulin (Figure 1). Moreover, the cost of regular insulin is significantly lower than fast-acting insulin. Therefore, if a similar (or better) glucose profile can be achieved with regular insulin-plus-pramlintide compared to fast-acting insulin-plus-pramlintide, then a co-formulation employing regular insulin should be prioritized.

[figure not shown]

Figure 1 Postprandial glucose profiles in type 1 diabetes following injections of regular insulin (left) or insulin lispro (right) plus either placebo or 60 μ g pramlintide bolus at meal (breakfast) time. Reprinted from the Symlin label [9].

Therefore, in this protocol, we aim to assess the effect of the simultaneous, closed-loop, basal-bolus infusion of pramlintide with insulin at a fixed ratio in controlling glucose levels. In the first experimental arm, we propose to infuse pramlintide with fast-acting insulin. In the second experimental arm, pramlintide will be infused with regular insulin. The control arm will be fast-acting insulin-alone closed-loop system.

2 Trial Objectives

The aim of the study is to assess the efficacy of the simultaneous, closed-loop, basal-bolus infusion of pramlintide with fast-acting insulin at a fixed ratio and pramlintide with regular insulin at a fixed ratio in controlling glucose levels compared to fast-acting insulin-alone closed-loop infusion. Pramlintide will be initiated for a minimum of 10 days with a target of 14 days before the closed-loop experiment,

which will mimic more closely the performance of the system during the chronic use of pramlintide rather than its acute use. Regular insulin will replace participant's usual insulin and will be initiated for a minimum of 10 days with a target of 14 days before the closed-loop experiment.

3 Hypothesis

Primary hypotheses:

1. During closed-loop control, the simultaneous basal-bolus infusion of pramlintide and fast-acting insulin improves glucose control compared to fast-acting insulin-alone infusion.
2. During closed-loop control, the simultaneous basal-bolus infusion of pramlintide and regular insulin improves glucose control compared to fast-acting insulin-alone infusion.

4 Study Design

4.1 Trial Design

This study is a randomized, three-way, crossover trial to compare the efficacy of **i)** fast-acting insulin-plus-pramlintide closed-loop delivery, **ii)** regular insulin-plus-pramlintide closed-loop delivery, and **iii)** fast-acting insulin-alone closed-loop delivery in regulating glucose levels over a period of 24 hours in a study on adults in inpatient settings. Insulin (fast-acting and regular) and pramlintide are given with fixed ratio (6 µg of pramlintide for each unit of insulin).

Before each 24-hour intervention visit, the participant's insulin therapy (basal rates and insulin-to-carbohydrate ratios) will be optimized for a minimum of 10 days, with a target of 14 days. If a participant is randomized to either rapid or regular insulin-plus-pramlintide arms, pramlintide will be infused using a second pump at a fixed ratio for a minimum of 10 days, and insulin therapy will be optimized. Regular insulin will replace participant's usual insulin and will be initiated for a minimum of 10 days, and insulin therapy will be optimized.

There will be a wash-out period of 0 to 42 days between the three intervention arms (termination of 24-hr intervention and start of next optimization period).

4.2 Study Population

The trial aims to enroll adult participants with type 1 diabetes using insulin pump therapy.

4.2.1 Inclusion criteria

To be eligible for the study, all participants must meet the following criteria:

1. Males and females \geq 18 years of age.
2. Clinical diagnosis of type 1 diabetes for at least 12 months.
The diagnosis of type 1 diabetes is based on the investigator's judgment; C peptide level and antibody determinations are not needed.
3. Insulin pump therapy for at least 6 months.
4. HbA1c \leq 10%.

4.2.2 Exclusion criteria

Participants who meet any of the following criteria are not eligible for the study:

1. Current or \leq 1 month use of other antihyperglycemic agents (SGLT2, GLP-1, Metformin, Acarbose, etc...).
2. Severe hypoglycemic episode within one month of admission.
3. Severe diabetes keto-acidosis episode within one month of admission.
4. Planned or ongoing pregnancy.
5. Known or suspected allergy to the study drugs.
6. Gastroparesis.
7. Use of prokinetic drugs that stimulate gastric emptying (domperidone, cisapride, metoclopramide).
8. Clinically significant nephropathy, neuropathy or retinopathy as judged by the investigator.
9. Recent ($<$ 6 months) acute macrovascular event e.g. acute coronary syndrome or cardiac surgery.
10. Current use of glucocorticoid medication.
11. Other serious medical illness likely to interfere with study participation or with the ability to complete the trial by the judgment of the investigator.
12. Failure to comply with team's recommendations (e.g. not willing to eat meals/snacks, not willing to change pump parameters, etc.).

4.3 Study Interventions

4.3.1 Fast Acting Insulin-alone closed-loop delivery

Variable subcutaneous insulin will be delivered to regulate glucose levels. Participants' usual fast-acting insulin (aspart, lispro, or glulisine) will be infused using a subcutaneous insulin infusion pump (Minimed® Veo™ or 630G, Medtronic). The participant will be wearing up to 2 glucose sensors, including Dexcom G4® or G5® (mandatory), and Abbott FreeStyle Libre (optional). The glucose level as measured by the Dexcom glucose sensor (Dexcom G4® or G5®, Dexcom, Inc.) will be entered manually into the computer every 10 minutes. The pumps infusion rates will then be changed manually based on the computer-generated recommendation. The computer-generated recommendations are based on a dosing algorithm [5]. Predictive algorithms have been successfully used in closed-loop studies in children, adolescents, pregnant women and adults [5]. The carbohydrate content for every

ingested meal will be entered into the algorithm to calculate the insulin prandial bolus. The carbohydrate content will be entered at the onset of the meal.

4.3.2 Fast-Acting Insulin-plus-pramlintide closed-loop delivery

Variable subcutaneous insulin and pramlintide will be delivered at a fixed ratio (6 µg pramlintide/unit insulin) to regulate glucose levels. Participants' usual fast-acting insulin (aspart, lispro, or glulisine) will be infused using a subcutaneous insulin infusion pump (Minimed® Veo™ or 630G, Medtronic). Basal-bolus pramlintide (AstraZeneca) will be infused using a second pump (Minimed® Veo™ or 630G, Medtronic). The participant will be wearing up to 2 glucose sensors, including Dexcom G4® or G5® (mandatory), and Abbott FreeStyle Libre (optional). The glucose level as measured by the Dexcom glucose sensor (Dexcom G4® or G5®, Dexcom, Inc.) will be entered manually into the computer every 10 minutes. The pumps' infusion rates will then be changed manually based on the computer-generated recommendation, while still maintaining the 6 µg/unit ratio. The computer-generated recommendations are based on a dosing algorithm [5]. The carbohydrate content for meals will be entered into the algorithm to calculate the prandial boluses for insulin. The carbohydrate content will be entered at the onset of the meal.

4.3.3 Regular Insulin-plus-pramlintide closed-loop delivery

Variable subcutaneous insulin and pramlintide will be delivered at a fixed ratio to regulate glucose levels. Regular insulin (Humulin R) will be infused using a subcutaneous insulin infusion pump (Minimed® Veo™ or 630G, Medtronic). Basal-bolus pramlintide (AstraZeneca) will also be infused using a second pump (Minimed® Veo™ or 630G, Medtronic). The participant will be wearing up to 2 glucose sensors, including Dexcom G4® or G5® (mandatory), and Abbott FreeStyle Libre (optional). The glucose level as measured by the Dexcom glucose sensor (Dexcom G4® or G5®, Dexcom, Inc.) will be entered manually into the computer every 10 minutes. The pumps' infusion rate will then be changed manually based on the computer-generated recommendation, without maintaining any specific infusion ratio of the two hormones. The computer-generated recommendations are based on a dosing algorithm [5]. The carbohydrate content for meals will be entered into the algorithm to calculate the prandial boluses for insulin.

5 Study Procedures and Visit Schedule

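### Section 4.3.3 tells staff both to keep and not to keep a fixed pramlintide-to-insulin ratio in the regular-insulin arm

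*Combined protocol and SAP*

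**What the plan says.** Section 4.3.3 describes the regular-insulin arm. Its first sentence reads "Variable subcutaneous insulin and pramlintide will be delivered at a fixed ratio to regulate glucose levels" and gives no number. Later in the same paragraph, the sentence on the manual pump adjustments ends "without maintaining any specific infusion ratio of the two hormones".

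The matching sentence for the fast-acting arm, in section 4.3.2, goes the other way: "infusion rates will then be changed manually based on the computer-generated recommendation, while still maintaining the" ratio of 6 µg/unit.

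Elsewhere the protocol is consistent:

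- Section 1 describes the planned infusion as "infusion of pramlintide and insulin with a fixed (i.e., mimicking co-formulation) in controlling glucose levels". The closing paragraph of that section again states the aim as "basal-bolus infusion of pramlintide with insulin at a fixed ratio in controlling glucose levels" and then names regular insulin as the second experimental arm.
- Section 2 names this arm in the aim: "pramlintide with regular insulin at a fixed ratio in controlling glucose levels".
- Section 4.1 covers both insulins, "Insulin (fast-acting and regular) and pramlintide are given with fixed ratio", at 6 µg per unit. For the run-in it says that, for participants "randomized to either rapid or regular insulin-plus-pramlintide arms, pramlintide will be infused using a second pump at a fixed ratio", this lasts at least 10 days.
- Section 6.1 says the procedures are the same at all three inpatient visits and that pramlintide follows insulin at a fixed ratio, changed every 10 minutes. The only difference it states for the regular-insulin visit is the 7:40 start.
- Section 8.1.1 sets 3 µg/U for the first 0–4 days of optimization, then 6 µg/U through the intervention visits, with no exception for any arm.

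**The concern.** This is a conflict in an operative dosing instruction for an arm that enters primary comparison ii (section 7.1.1). Section 4.3.3 is the arm-specific description of the intervention, so staff could reasonably look there for the rule. The rates are set by hand.

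Staff who followed the clause would cause four problems:

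1. The arm would not deliver the infusion that sections 1 and 2 set out to test, namely one that mimics a co-formulation.
2. The pramlintide rule would change on the day of measurement, after at least 10 days of optimization at a set ratio in the same arm.
3. No replacement rule is given. Section 4.3.3 describes the meal calculation as producing insulin boluses, and section 1 describes the algorithm as controlling insulin. Without the ratio, the pramlintide dose has no stated basis.
4. Secondary comparison 1 (section 7.1.2), which sets the two pramlintide arms against each other, would no longer isolate insulin type. Section 1 relies on that contrast when it argues that a regular-insulin co-formulation should be prioritized if its glucose profile is similar or better.

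The text also leaves it unclear whether a departure from 6 µg/U at this visit would be a protocol deviation.

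**Working it through.** **The plan's own figure.** The only related number is the sample size in section 7.2, and this point does not dispute it. With a difference of 7 points, an SD of differences of 10 and alpha 0.05/2 = 0.025 (two-sided assumed, since sidedness is not stated), the normal approximation gives (10 × (2.241 + 0.842) / 7)² = 19.4, so 20. The exact paired t-test gives n = 22 with power 0.800, which matches the plan. With 28 completers the power would be 0.901. None of this depends on the ratio wording.

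**The statements side by side, for the regular-insulin arm.**

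| Place | Rule | Names this arm? | Gives 6 µg/U? |
|---|---|---|---|
| Section 1, closing aim | fixed | no | no |
| Section 2, aim | fixed | yes | no |
| 4.1, ratio sentence | fixed | yes | yes |
| 4.1, optimization sentence | fixed | yes | no |
| 4.3.3, first sentence | fixed | yes | no |
| 6.1, visit procedures | fixed | no | no |
| 8.1.1, lead sentence | fixed | no | no |
| 8.1.1, second bullet | fixed | no | yes |
| 4.3.3, pump-adjustment clause | no specific ratio | yes | no |

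Eight statements in six sections support a fixed ratio. Four of them name this arm and two give 6 µg/U. One clause says the opposite.

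**Can the two be reconciled?**

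- *The 3 µg/U step in 8.1.1.* It applies only to the first 0–4 days of optimization, so it does not explain a free ratio at the visit.
- *A deliberate exception for this arm.* It would contradict section 2, section 4.1, section 6.1, section 8.1.1 and the first sentence of 4.3.3 itself. Section 6.1 states the 7:40 start as a difference for this visit but no difference in dosing.
- *A reading limited to the algorithm's recommendation.* The clause is about how the pump rates are changed, which is the same step that 4.3.2 ties to 6 µg/unit.

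No other text resolves the conflict.

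**How much of the visit the clause covers.** Rates are updated every 10 minutes:

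- 24 hours: 1,440 min / 10 = 144 changes.
- From 7:40 to 8:00 the next morning: 1,460 min / 10 = 146 changes.

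**The case against.** The strongest reply accepts the contradiction and disputes its weight. Section 8.1.1 is the dedicated administration section and is unambiguous for the intervention visits. Section 4.1 names regular insulin and gives the number. Since the clause offers no other way to dose pramlintide, staff would probably fall back on 6 µg/U. Every harm depends on staff preferring one clause over several clear statements, and the documents do not show that they would. Hypothesis 2 and primary comparison ii mention no ratio, so neither is contradicted by its own wording.

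Most of this stands as a limit on the consequence. The harm is conditional, and the conflict is with the stated aim and the dosing sections rather than with the wording of the primary comparison. Falling back on 6 µg/U is plausible but is an inference: the computer's recommendation could be read as covering both pumps, and the same gap can be read as leaving the pramlintide dose undefined.

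The tally can also be made smaller. The 4.1 optimization sentence governs the run-in, 8.1.1 is counted twice, and the section 1 aim is general. Counting once per section, and only text that reaches this arm's visit, leaves five: sections 2, 4.1, 4.3.3 (first sentence), 6.1 and 8.1.1. Five against one supports the same conclusion.

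Finally, 4.3.3 departs from 4.3.2 in two places: it omits the number and reverses the clause. Leftover text is the likelier explanation, but intent cannot be excluded. That is a reason to ask before editing and does not justify leaving the text alone.

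**Conclusion.** The concern holds. Section 4.3.3 contradicts itself and the rest of the protocol on pramlintide dosing in one of three arms. The clause is the outlier, and the weight of the text supports 6 µg/U at the regular-insulin visit. It should be fixed, because it is a live dosing instruction covering 144 to 146 manual rate changes per visit in an arm that feeds a primary comparison.

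The size of any effect on time in range cannot be derived from the documents. Alpha, power and the sample size are unchanged. That the clause is a drafting error is an inference from the surrounding text, and the documents do not show which instruction staff would follow.

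**What to change.** Ask the investigator to confirm that 6 µg/U is the rule for this arm. Then, in section 4.3.3:

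- replace the clause with the wording used in 4.3.2, which keeps the 6 µg/unit ratio when pump rates are changed;
- add the 6 µg pramlintide per unit insulin figure to the first sentence, as 4.3.2 does.

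If a free ratio was in fact intended, the larger edit is needed: sections 1, 2, 4.1, 6.1, 8.1.1 and the opening of 4.3.3 would have to change, and the pramlintide dosing rule would have to be written down.

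The expected correction costs one clause and one parenthesis, with no added participants, procedures or analysis changes. Section 9.5 requires the ethics committee to be informed of amendments and administrative changes, so that notice is part of the cost.

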5.1 Recruitment

Potential participants will be recruited at the McGill University Health Centre - Adult Diabetes Clinic, Montréal, Canada. A total of 28 participants will be enrolled in the study. The study will be conducted at the Centre for Innovative Medicine (CIM) at McGill University Health Centre Research Institute,

Montréal, Canada. Participants showing interest in participation will have the study fully explained to them and will be offered the opportunity to ask questions. Interested participants that meet basic eligibility criteria will be scheduled for the admission visit.

5.2 Visit Schedules

5.2.1 Admission Visit (Visit 1)

At the admission visit, the following procedures will be taken:

- Participants will sign the consent form.
- Inclusion and exclusion criteria will be assessed
- A medical visit will be taken to establish medical history (i.e. recent severe hypo- and hyperglycemia episodes, micro- and macrovascular complications, comorbidities and precise list of all medications).
- Records of current insulin therapy (total daily dose, carbohydrate to insulin ratios, basal rates, insulin sensitivity, target blood glucose levels and active insulin time).
- A1c level if no recent (\leq 1 month) result is available.
- For women for childbearing potential, a pregnancy test will be performed
 - Women 50 years or older with an absence of menstrual bleeding for the past year will not be required to take the pregnancy test.
 - Women that underwent hysterectomy will not be required to take the pregnancy test.
- Serum creatinine and eGFR level if no recent (\leq 1 month) results are available.
- Weight and height measurements will be obtained.
- Participants will complete a questionnaire on the awareness of hypoglycemia.

5.2.2 Initiation Optimization Visit (Visit 2)

At initiation optimization visit, the following procedures will be taken:

- Participant will receive training on the study material (glucose sensor, insulin pump and artificial pancreas).
- Any question concerning the optimization period or the intervention visit will be answered.
- Indications regarding the use of regular insulin and pramlintide will be given to the participant.
- If the participant is using a pump other than Medtronic, the participant will receive a study pump (Minimed® Veo™ or 630G, Medtronic) to infuse rapid insulin and regular insulin. The patient may switch to the study pump for the optimization period or continue using their own pump. The patient will be responsible for making the switch to the study pump on their own, at least 1 day prior to the intervention.

- Participants will receive pramlintide, second pump (Minimed® Veo™ or 630G, Medtronic) and second catheter for infusion of pramlintide. Infusion of pramlintide will be initiated as per the optimization schedule, and may require the patient to initiate it on their own, outside of visit 2.
- A glucose sensor (Dexcom G4® or G5®, Dexcom, Inc.) will be provided. The patient may be required to insert the sensor on their own, outside of visit 2, as per the optimization schedule.
- Optionally, if the patient consents to wearing two glucose sensors, an additional sensor (FreeStyle Libre, Abbott) will be provided by the research team and training on the sensor use will be provided by a trained research member.
 - Installation of FreeStyle Libre sensor will take place either **i)** 0-2 days **ii)** 6-8 days or **iii)** 11-13 days prior to the intervention. The sensor installation schedule will be determined by a member of the research team.

After this visit, the treatment optimization for a minimum of 10 days will be conducted.

5.2.3 Intervention visits (Visit 3, 4 and 5)

After the optimization period, each study participant will be admitted to our clinical research facility for a 24-hour intervention. Details of intervention visits are presented in subsequent sections.

5.3 Randomization

Each study participant will be assigned a unique anonymous identification number, which will be used throughout the study. A blocked balanced randomization will be used to determine the order of the interventions.

Participants will be randomized to either **i)** fast-acting insulin-plus-pramlintide closed-loop delivery, **ii)** regular insulin-plus-pramlintide closed-loop delivery, and **iii)** fast-acting insulin-alone closed-loop delivery.

Randomization envelopes will be opened after admissions visit 1.

5.4 Treatment Optimization

The optimization period will last for a minimum of 10 days, with a target of 14 days. During this optimization period, each participant will wear a glucose sensor. A research team member will contact (by phone or email) study participants in order to optimize their treatment parameters (insulin to carbohydrate ratios, basal rates, etc.). The insulin dose will be titrated to meet target glucose according to the continuous glucose sensor. Research team might ask study participants to present in person if deemed necessarily for treatment optimization. In addition, gastrointestinal symptoms (nausea, vomiting, bloating, and heart burn) will be evaluated during the optimization period, and during the

inpatient interventions. Intervention visits will be conducted after this optimization period. Similar contact and therapy optimization procedure will be applied prior to each intervention.

During days when participant will be wearing the CGM sensor he should be advised to avoid consumption of drugs containing acetaminophen due to possible effect on accuracy of glucose readings. If acetaminophen is part of the subject's standard therapy, the study physician will discuss alternative treatments with the participant.

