6.1.1 Initial procedures (7:00-8:00)

- Participants will be admitted at the MUHC Research Institute Centre for Innovative Medicine (CIM) around 7:00.
- Participant's weight will be obtained.
- For women for childbearing potential, a pregnancy test will be performed
 - Women 50 years or older with an absence of menstrual bleeding for the past year will not be required to take the pregnancy test.
 - Women that underwent hysterectomy will not be required to take the pregnancy test.
- Revision of inclusion and exclusion criteria
- Revision of the patient's medication
- A cannula will be inserted into the antecubital or hand vein for blood sampling purposes.
- Participants will be asked to calibrate the glucose sensor using their capillary glucose level as measured by their meter.
- Presence of gastrointestinal symptoms (nausea, vomiting, bloating, and heart burn) will be assessed in the fasting state.
- The closed-loop study will begin at 7:40 (regular insulin) or 8:00 (rapid insulin).

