6.1.3 Procedures related to Lunch (12:00)

At 12:00, a mixed meal will be served containing 50g – 80g of carbohydrates. The carbohydrate content will be entered at the onset of the meal. Participants will have a choice to personalize the content of their meal from a menu of four main options. Study participants will consume the same meal at each visit. Presence of gastrointestinal symptoms (nausea, vomiting, bloating, and heart burn) will be assessed in the post-prandial period.

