7.1.2 Secondary endpoints and comparisons

1. Percentage of time of glucose levels spent in target range, comparing fast-acting insulin-plus-pramlintide closed-loop delivery vs. regular insulin-plus-pramlintide closed-loop delivery.
2. Percentage of time (8:00-8:00) of glucose levels spent:
 - a.* between 3.9 and 7.8 mmol/L; *b.* between 3.9 and 10 mmol/L; *c.* below 3.9 mmol/L; *d.* below 3.3 mmol/L; *e.* below 2.8 mmol/L; *f.* above 7.8 mmol/L; *g.* above 10 mmol/L; *h.* above 13.9; *i.* above 16.7 mmol/L.
3. Percentage of overnight time (23:00-8:00) of glucose levels:
 - a.* between 3.9 and 7.8 mmol/L; *b.* between 3.9 and 10 mmol/L; *c.* below 3.9 mmol/L; *d.* below 3.3 mmol/L; *e.* below 2.8 mmol/L; *f.* above 7.8 mmol/L; *g.* above 10 mmol/L; *h.* above 13.9; *i.* above 16.7 mmol/L.
4. Standard deviation of glucose levels as a measure of glucose variability.
5. Total insulin delivery.
6. Total pramlintide delivery.
7. Mean glucose level during: *a.* the overall study period; *b.* overnight period.
8. Mean insulin concentration.
9. Mean glucagon concentration.
10. Mean amylin concentration.
11. Number of participants experiencing hypoglycemia requiring oral treatment during: *a.* the overall study period; *b.* the night.
12. Gastrointestinal symptoms during the treatment optimization (i.e., the minimum 10 days prior to the 24-hour closed-loop visits) and during the 24-hour closed-loop visits.

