8.1.2 Potential Risks

Pramlintide can cause the following side effects [9]:

- Severe low blood glucose level
- Nausea
- Vomiting
- Stomach pain
- Decreased appetite
- Headache
- Injection site reactions, including bruising, swelling or itching at the injection site.

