10.1 Adverse Events (AE)

An adverse event is any untoward medical occurrence or unfavorable and unintended sign in a subject administered a pharmaceutical product, biologic (at any dose), or medical device, whether or not considered related to the use of that product. This includes the onset of new illness and the exacerbation of pre-existing conditions.

Additionally, any event that is associated with or observed in conjunction with a product overdose (whether accidental or intentional) or a product abuse and/or withdrawal is also considered an adverse event. Adverse event is considered also malfunction or lack of function of any software or hardware part of the artificial pancreas system which results in symptoms.

The onset and end dates, severity and relationship (causality) to study drug/device/procedure will be recorded for each adverse event. Any action (treatment) or outcome (e.g., hospitalization, discontinuation of therapy, etc.) will also be recorded for each AE.

Adverse events will be collected from the time of signing the informed consent until the subject finishes his/her participation in the study, including non-interventional days.

After the last per-protocol contact the investigator does not need to actively monitor patients for AEs. However, if the investigator becomes aware of SAEs that occurred after the last per protocol contact and if there is suspected causal relationship to the study intervention, the SAEs will be reported by the investigator.

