10.3 Severity (intensity) and causality of adverse events

Adverse events will be classified as mild, moderate or severe in severity (intensity) as follows:

- Mild: Discomfort noticed but no disruption of normal daily activity.
- Moderate: Discomfort sufficient to reduce or affect normal daily activity.
- Severe: Incapacitating with inability to work or perform normal daily activity

Adverse events will be at the same time classified assessed for causality to the study intervention. Medical judgement should be used to determine the relationship, considering all relevant factors, including pattern of reaction, temporal relationship, de-challenge or re-challenge, confounding factors such as concomitant medication, concomitant diseases and relevant history.

- Yes: There is a reasonable causal relationship between the investigational product administered and the AE.
- No: There is no reasonable causal relationship between the investigational product administered and the AE.

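### The solicited symptom list behind secondary endpoint 12 omits stomach pain and decreased appetite, both of which the protocol lists as pramlintide effects

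*Combined protocol and SAP*

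**What the plan says.** Section 5.4 (Treatment Optimization) states that "gastrointestinal symptoms (nausea, vomiting, bloating, and heart burn) will be evaluated during the optimization period" and extends this to the inpatient stays. It does not say how the answers are recorded, whether they are graded, or how often the questions are put.

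At each 24-hour visit the same four items are used five times. Section 6.1.1 (Initial procedures) has "Presence of gastrointestinal symptoms (nausea, vomiting, bloating, and heart burn) will be assessed in the fasting state". Sections 6.1.2 to 6.1.5 then repeat one sentence for breakfast, lunch, dinner and the bedtime snack, for example in 6.1.3: "Presence of gastrointestinal symptoms (nausea, vomiting, bloating, and heart burn) will be assessed in the post-prandial period".

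Section 8.1.2 (Potential Risks) gives seven pramlintide side effects. Four concern the gut or appetite: nausea, vomiting, stomach pain and "Decreased appetite".

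Section 7.1.2, item 12, takes as its endpoint "Gastrointestinal symptoms during the treatment optimization" and during the 24-hour visits. It gives no symptom list, scale or summary measure.

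Adverse events follow a separate route. Section 10.1 says "An adverse event is any untoward medical occurrence or unfavorable and unintended sign in a subject", and "The onset and end dates, severity and relationship (causality) to study drug/device/procedure will be recorded for each adverse event". Section 10.3 supplies three grades, the middle one being "Moderate: Discomfort sufficient to reduce or affect normal daily activity".

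**The concern.** A checklist fixes which symptoms every participant is asked about, in every arm, in the same way. A symptom left off it is heard of only if someone raises it. Here the omitted items are two that the protocol itself attributes to the drug under test, and no reason is given for the difference between the two lists.

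The rationale in Section 1 is that pramlintide is under-used and that delivery alongside insulin could widen its uptake. How well basal-bolus infusion is tolerated bears directly on that case, and endpoint 12 is the only planned comparison that speaks to it. If two expected effects reach the endpoint only by chance, the tolerability result may look better than it should. If presence is all that is recorded, a brief mild episode and an incapacitating one also look alike at that assessment.

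**Working it through.** **1. The two lists side by side.**

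| Symptom | Listed as a pramlintide effect (8.1.2) | Asked about (5.4; 6.1.1 to 6.1.5) |
|---|---|---|
| Nausea | yes | yes |
| Vomiting | yes | yes |
| Stomach pain | yes | no |
| Decreased appetite | yes | no |
| Bloating | no | yes |
| Heartburn | no | yes |

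The checklist covers 2 of the 4 gut or appetite effects in Section 8.1.2. That section does not group its items, so the count depends on classing appetite with the gut. Without appetite, the checklist covers 2 of 3 and misses stomach pain.

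**2. Form of record.** All five inpatient assessments (one fasting, four post-prandial) refer to presence only. Section 5.4 uses a broader verb and leaves the format open. The optimization period lasts at least 10 days per arm, against one day for the visit, so the format is unspecified for most of the time that endpoint 12 covers.

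**3. The second route.** Section 10.1 collects adverse events from consent to the end of participation, which includes the optimization periods. The only stated restriction on what is recorded is for hypoglycemia short of severe (Section 10.2). Stomach pain, and appetite loss if regarded as untoward, can therefore be captured with dates, grade and causality. Two things limit this route as a substitute:
- Section 10.1 describes no active questioning.
- Section 7 contains no comparison of adverse events by arm. Section 7.4 names methods for continuous endpoints and for the number treated for hypoglycemia, and neither clearly applies to endpoint 12.

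**4. Size.** The documents give no rate for any of these symptoms, so the shortfall cannot be derived. As an illustration, let q be the assumed proportion of participants in an arm whose only symptom is an unlisted one. With all 28 participants observed in that arm, the number the checklist misses is 28 × q:
- q = 5%: 28 × 0.05 = 1.4
- q = 10%: 28 × 0.10 = 2.8
- q = 20%: 28 × 0.20 = 5.6

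These are upper figures for each q, because some of these participants may be picked up as adverse events.

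**5. What is not touched.** The plan's only power figure concerns the primary endpoint, and it reproduces. For a paired t-test with a difference of 7 points, SD 10 and two-sided alpha 0.025, the noncentrality at n = 22 is (7/10) × √22 = 3.28 and the power is 0.800. At n = 28 the power is 0.901. The plan does not state that the test is two-sided, but a one-sided test would need only 19. Nothing in this point changes these figures.

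**The case against.** The strongest reply is that the trial already has a full adverse event system with three severity grades and causality, running throughout. That stands against a broader reading: a reader might infer that pramlintide intolerance goes unmeasured in the trial as a whole, or that mild and incapacitating nausea are nowhere told apart. Sections 10.1 and 10.3 do not support that. The system reduces the gap in endpoint 12 but does not close it, for the two reasons in step 3.

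Second, a reader might infer that presence is all that is recorded throughout. That wording belongs to the inpatient visits. For optimization the defect is an unstated format.

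Third, endpoint 12 has no scoring rule, so it cannot be said that a participant with stomach pain would be counted as free of symptoms. Nothing bars adding a volunteered symptom. Equally, nothing provides for it, and the only list the plan supplies leaves it out.

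Fourth, decreased appetite may be seen as the drug acting as intended, since Sections 1 and 8.1 describe increased satiety as an action of amylin. This is a fair reason not to pool it with intolerance, and the fix respects it. It also makes it less certain that appetite loss would be reported as untoward. Bloating and heartburn are sensible items, given the slowed gastric emptying described in the same sections, and should stay.

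Finally, it is tempting to say that an appetite question would explain low glucose after meals, because the carbohydrate amount is entered when the meal starts. It would not: that needs the carbohydrate actually eaten, which an appetite item does not measure.

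**Conclusion.** The point holds in a limited form. The solicited list omits two effects that Section 8.1.2 attributes to pramlintide, and the same omission occurs wherever the list appears. Stomach pain and decreased appetite are likely to be under-ascertained in endpoint 12. This assumes that the stated list is followed as written and that volunteered reports are less complete than answers to a direct question.

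The amount is unknown. The range of 1.4 to 5.6 participants out of 28 rests on the assumed 5% to 20% and on no capture as adverse events. A reader might go further and quote a percentage understatement, or place the loss almost wholly in the two pramlintide arms. The documents give no base rate and no rates by arm, so neither claim is supported.

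One secondary endpoint is affected. The change is worth making because it is cheap and concerns the only planned comparison of gastrointestinal tolerability.

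**What to change.** - In Section 5.4 and Sections 6.1.1 (Initial procedures) to 6.1.5, add stomach pain and decreased appetite to the four existing items, and ask all six in all three arms.
- Grade each reported symptom as mild, moderate or severe on the scale in Section 10.3, at the inpatient assessments and during optimization. This also settles the format that Section 5.4 leaves open.
- In Section 7.1.2, item 12, report by arm the number of participants with any symptom and the number with any moderate or severe symptom, separately for the optimization period and the 24-hour visit.
- Report decreased appetite on its own line, because increased satiety is a stated action of the drug.

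The cost is two more items and a grade at contacts already planned, with a change to the case report form. Questioning takes slightly longer, and the reported symptom rate may look less favourable. No treatment rule, primary endpoint or sample size changes.
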